## IV. General Methodology

---

Definition of Statistical Significance: The statistical plan will test non-directional hypotheses, i.e., all tests will be 2-sided. The level of significance for all efficacy and safety analyses will be 0.05.

Statistical Tests: For situations where one observation per patient is observed, (e.g. safety comparisons at individual time points), a general analysis convention will be used unless otherwise specified. For continuous and ordinal variables, treatment group differences will be tested using the Wilcoxon rank-sum test for two groups and Kruskal-Wallis one-way analysis of variance for comparisons of more than two groups. For censored data, like time to event, treatment group differences will be tested using the log rank test. For discrete variables, treatment group differences will be tested using the chi-square test. In the situation of low cell counts the treatment group differences will be tested using Fisher's exact method.

Descriptive Statistics: For continuous and ordinal variables the number of observations, number of missing values, mean, standard deviation, median, twenty-fifth percentile, and seventy-fifth percentile will be given. For binary (e.g. yes/no), categorical, and/or ordinal variables a simple count and percent will be provided. Other statistics may be considered if necessary.

Descriptive Plots: Descriptive plots may be produced in addition to descriptive statistics if deemed appropriate. If deemed necessary plots of descriptive statistics such as spaghetti, mosaic, box, cumulative distribution, and loess curves will be provided.

Study Listings: Study data will be listed by treatment group, visit if applicable, and patient where appropriate.

Software and Validation Procedures: All data presented in interim and final analyses will be generated and validated under the guidance of the DCRI Clinical Trials Statistical SOPs.

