11. STATISTICAL CONSIDERATIONS

11.1 Overview

Means, standard deviations, medians, 25th and 75th percentiles will be presented for continuous variables; the number and frequency of patients in each category will be presented for nominal variables. Statistical tests with a two-sided p value <0.05 will be considered statistically significant, unless otherwise stated. Analyses will be performed using SAS software (SAS Institute, Inc., Cary, NC).

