## VI. Secondary Endpoints

---

Secondary goals of this study are to assess differences between treatment groups for the following:

1. Time to death from any cause
2. Time to first non-elective respiratory hospitalization
3. Time to first non-elective all-cause hospitalization
4. Total number of non-elective respiratory hospitalizations
5. Total number of non-elective all-cause hospitalizations
6. Change in FVC from randomization to 12 months
7. Change in DLCO from randomization to 12 months
8. Total number of respiratory infections
9. Change in UCSD-Shortness of Breath Questionnaire from randomization to 12 months
10. Change in Fatigue Severity Scale score from randomization to 12 months
11. Change in Leicester Cough Questionnaire score from randomization to 12 months
12. Change in EQ-5D score and SF-12 score from randomization to 12 months
13. Change in ICEpop CAPability measure for Older people (ICECAP-O) score from randomization to 12 months

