## XII. Interim Analyses

---

There will be one planned interim review for efficacy. The efficacy review will focus on the composite endpoint of respiratory hospitalization or all-cause death and should occur once 300 enrolled subjects have been followed for 12 months. The information time will be computed by dividing the observed number of primary endpoint events by the projected number of primary endpoint events. To conserve the overall type I error rate of 0.05 the O'Brien-Fleming Spending Function will be used to allow for stopping if large treatment effects are observed while allowing the final significance level to be conserved at the nominal level (Lan and DeMets 1983).

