## XIII. Subgroup of Interest

---

The following subgroups of interest will be based on information available prior to randomization:

- Use of standard of care medications at enrollment
- Antimicrobial therapy determined prior to randomization
- Use of NAC at enrollment

The subgroups of interest will be assess sepeareately for the primary endpoint within the framework of cox proportional hazards regression model. The subgroup variable and subgroup by treatment arm intereaction will be added to the model. If the interaction is significant then the hazard ratios and 95% confidence intervals will be

estimated for the difference in treatment arms for the separate levels of the subgroup variable.

The antimicrobial therapy determined prior to randomization is made up to 2 groups: 1) Co-trimoxazole and 2) Doxycycline. The baseline and primary/secondary analyses will be repeated for these 2 groups separately.

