## XV. Tables / Listing / Graph Mock-ups

---

The tables, listings, and figures shown below are the template versions and may be modified as needed. It is planned that there will be separate sets of tables based on the subgroups of interest listed above.

**CLEANUP-IPF Study  
Final Analysis Table 1.1  
Enrollment and Patient Follow-up  
Patient Enrollment by Site**

Investigational Site	Enrolled
(101) <<Site name>>	N/N (xx.x%)
(102) <<Site name>>	N/N (xx.x%)
(103) <<Site name>>	N/N (xx.x%)
(104) <<Site name>>	N/N (xx.x%)
...	...
(140) <<Site name>>	N/N (xx.x%)
Total	N/N (xx.x%)

[figure not shown]
**CLEANUP-IPF Study  
Final Analysis Table 1.2  
Enrollment and Patient Follow-up  
Completed and Withdrawn Patients**

Event	Oral antimicrobial therapy N= N NEVAL	Standard Care N= N NEVAL	All Patients N= N NEVAL	P-Value
Started Study	N	N	N	
Completed	N/N (xx.x%)	N/N (xx.x%)	N/N (xx.x%)	
Study Termination due to Death	N/N (xx.x%)	N/N (xx.x%)	N/N (xx.x%)	
Withdrawal				
6 Months				x.xxx
# of Events/# of Patients	N/N	N/N	N/N	
Kaplan-Meier Event Rate (95% CI)	xx.x (xx.x, xx.x)	xx.x (xx.x, xx.x)	xx.x (xx.x, xx.x)	
12 Months				x.xxx
# of Events/# of Patients	N/N	N/N	N/N	
Kaplan-Meier Event Rate (95% CI)	xx.x (xx.x, xx.x)	xx.x (xx.x, xx.x)	xx.x (xx.x, xx.x)	
18 Months				x.xxx
# of Events/# of Patients	N/N	N/N	N/N	
Kaplan-Meier Event Rate (95% CI)	xx.x (xx.x, xx.x)	xx.x (xx.x, xx.x)	xx.x (xx.x, xx.x)	
24 Months				x.xxx
# of Events/# of Patients	N/N	N/N	N/N	
Kaplan-Meier Event Rate (95% CI)	xx.x (xx.x, xx.x)	xx.x (xx.x, xx.x)	xx.x (xx.x, xx.x)	
Reasons for Withdrawal				
Reason #1	N	N	N	
Reason #2	N	N	N	
...	...	...	...	
Reason #X	N	N	N	
Therapy Distribution				
6 Months	N/N (xx.x%)			
12 Months	N/N (xx.x%)			
Therapy adherence (7 Days Prior)				
6 Months	N/N (xx.x%)			
12 Months	N/N (xx.x%)			
Therapy crossover				

**CLEANUP-IPF Study  
Final Analysis Table 1.2  
Enrollment and Patient Follow-up  
Completed and Withdrawn Patients**

Event	Oral antimicrobial therapy N= N NEVAL	Standard Care N= N NEVAL	All Patients N= N NEVAL	P-Value
6 Months				
# of Events/# of Patients		N/N		
Kaplan-Meier Event Rate (95% CI)		xx.x (xx.x, xx.x)		
12 Months				
# of Events/# of Patients		N/N		
Kaplan-Meier Event Rate (95% CI)		xx.x (xx.x, xx.x)		
18 Months				
# of Events/# of Patients		N/N		
Kaplan-Meier Event Rate (95% CI)		xx.x (xx.x, xx.x)		
24 Months				
# of Events/# of Patients		N/N		

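### SAP IV judges all 14 secondary scores at 0.05 each, unadjusted and unordered, and SAP XIII repeats them by agent: up to about a 51% chance of a false positive among the overall tests

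*SAP*

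**What the plan says.** SAP IV sets one rule for everything: "all tests will be 2-sided" and "The level of significance for all efficacy and safety analyses will be 0.05". Protocol 11.1 agrees: "Statistical tests with a two-sided p value <0.05 will be considered statistically significant, unless otherwise stated". For the secondary endpoints, neither document states otherwise.

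SAP VI lists the secondary endpoints up to number 13 ("13. Change in ICEpop CAPability measure for Older people (ICECAP-O) score from randomization to 12 months"). Item 12 holds two instruments ("Change in EQ-5D score and SF-12 score from randomization to 12 months"), so there are at least 14 tests. Neither document gives an order, a gate on the primary result, an adjusted level or a statement that these results are exploratory.

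On subgroups, SAP XIII reports level-specific hazard ratios for the primary endpoint only after a significant interaction. It then says of the two agents: "The baseline and primary/secondary analyses will be repeated for these 2 groups separately". No interaction condition attaches to that repeat. SAP XV adds: "It is planned that there will be separate sets of tables based on the subgroups of interest listed above".

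Type I error is controlled in one place, the single interim look at the primary composite: "To conserve the overall type I error rate of 0.05 the O'Brien-Fleming Spending Function will be used" (SAP XII; likewise Protocol 13.2).

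**The concern.** Applied as written, the rule lets any one of many correlated, unadjusted tests be called significant, including a single questionnaire within a single agent group. The trial is unblinded (Protocol 5.2), and six of the 14 scores are patient questionnaires. The letter at the end of the SAP records that the trial stopped for futility on the primary endpoint. Secondary and agent-specific results are therefore where a positive claim could still be made. The same letter mentions trends against the intervention, so a chance finding of harm on a secondary endpoint would be equally open to over-reading. What is at stake is how secondary and agent-specific results may be described, not the primary result.

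**Working it through.** **The plan's own figures.** The documents give no family-wise error for the secondary endpoints, so there is nothing to reproduce directly. What can be checked is where the design's 0.05 goes. Protocol Table 2, hazard ratio 0.65, 80% power: 4 × (1.960 + 0.842)² / (ln 0.65)² = 31.40 / 0.1856 = 169 events, as stated. At 90% power the same formula gives 226, as stated. The full two-sided 0.05 is assigned to the primary comparison.

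**Inputs.**
- Level: 0.05 two-sided per test (SAP IV, Protocol 11.1).
- Number of overall secondary tests: 13 items, 14 scores (SAP VI).
- Repeats: two agent groups (SAP XIII), so 14 × 3 = 42 tests in all.
- Correlation between test statistics: not in the documents. Assumed common values from 0 to 0.7 are shown.
- Split of patients between agents: not in the documents. Assumed 50/50 and 70/30; the choice hardly changes the result.

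**Step 1, independence, no effect anywhere.** 1 − 0.95^14 = 0.512 (for 13 tests, 1 − 0.95^13 = 0.487). Expected false positives: 14 × 0.05 = 0.70. For jointly normal two-sided statistics, independence is the worst case, so about 51% is a ceiling.

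**Step 2, favourable direction only.** 1 − 0.975^14 = 0.298.

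**Step 3, correlated statistics.** Simulated equicorrelated normal statistics for the 14 overall tests.

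**Step 4, agent-group repeats.** The two agent groups hold separate patients. Their 28 tests alone give 1 − 0.95^28 = 0.762 if endpoints are independent. Each overall statistic was then added as the weighted sum of its two agent-group statistics, so the overall test is correctly correlated with its parts. Expected false positives: 42 × 0.05 = 2.1.

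| Assumed correlation between endpoints | 14 overall tests, either direction | 14 overall tests, favouring treatment | 42 tests, either direction |
|---|---|---|---|
| 0 | 51% | 30% | 82% |
| 0.3 | 44% | 22% | 74% |
| 0.5 | 35% | 17% | 63% |
| 0.7 | 25% | 12% | 48% |

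For the 42 tests at correlation 0.5, the favourable-direction figure is 35%.

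**Step 5, a structured alternative.** Assume correlations of 0.5–0.8 among death and hospitalization endpoints, 0.3–0.5 for lung function, 0.3–0.6 among questionnaires, and 0.1–0.3 between these blocks. The 14 overall tests then give 36% to 46% in either direction and 18% to 25% in favour of treatment.

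**The case against.** The strongest reply is that the primary conclusion is safe: there is one primary endpoint, with O'Brien-Fleming spending for its one interim look. That stands. A reader might infer from SAP IV that the plan has no error control at all; SAP XII shows otherwise.

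A reader might also infer that a false-positive secondary result is likely. For the 14 overall tests the documents do not support that. Items 1 to 5 are overlapping death and hospitalization outcomes, in first-event and count versions, so independence is unrealistic and the chance is below one half. For a false benefit claim, the relevant figure is about half of that again. It passes one half only when the agent-group repeats are counted, and then only up to a correlation somewhere between 0.5 and 0.7.

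It is tempting to count every p-value cell in the mock-up tables. That count would mix in primary-endpoint cells, several versions of one measure, and cells that the templates do not print. SAP XV also says the templates may be modified. Template cells are not a family of claims.

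The model-table shells head their p-value column as nominal. This is a weak caveat: the primary endpoint sits under the same header, no rule of interpretation goes with it, and the descriptive tables do not use the word.

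Two further points stand. Eight of the 14 scores are not questionnaires, and hospitalizations go to blinded adjudicators (Protocol 9.3). Adjusting safety tests would reduce sensitivity to harm, so they should not be adjusted.

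**Conclusion.** The concern holds for the secondary endpoints and their agent-group repeats. SAP IV is an explicit rule, not merely silence, and it labels as significant any secondary p below 0.05. Under no effect, the chance of at least one such result among the 14 overall tests is at most about 51%, and about 25% to 44% at assumed correlations of 0.7 to 0.3. About half of that favours treatment. With the ungated agent-group repeats it is about 48% to 82% over assumed correlations of 0.7 to 0. The counts and the level come from the documents; the correlations are assumptions.

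The primary conclusion is not affected. That secondary claims may be made whatever the primary shows is an inference from the absence of a gate; neither document says so. The change should be made because it settles what the trial may claim, at almost no cost.

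**What to change.** Replace the SAP IV sentence on the significance level with:

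> The two-sided 0.05 level, with O'Brien-Fleming spending for the interim look, applies to the primary endpoint. Secondary, agent-specific and time-point comparisons are exploratory and are reported as estimates with 95% confidence intervals; their p-values are nominal and unadjusted and support no claim of significance. Subgroup interaction tests use a nominal 0.05 only to trigger reporting of level-specific hazard ratios. Safety comparisons keep an unadjusted nominal 0.05 as a descriptive flag, so that sensitivity to harm is not reduced.

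The last two sentences are needed. Without them, the interaction trigger in SAP XIII and the chi-square tests in SAP IX would have no stated level.

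In the table shells, label every p-value column other than the primary as nominal. Deleting those columns is optional.

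Cost: the replacement text above and relabelled columns, with no new data and no change to the primary analysis. Downside: no formal claim from a secondary endpoint. If one were wanted, it would need a pre-specified adjustment instead, for example a Bonferroni level of 0.05 / 14 = 0.0036 per test, which holds the family-wise error at or below 5% under any correlation for the 14 overall tests.

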## V. Primary Endpoint

---

The primary endpoint of this study will be the comparison of "Standard care + oral antimicrobial therapy" and "Standard care" for the time to first non-elective, respiratory hospitalization or all-cause mortality.

## VI. Secondary Endpoints

---

Secondary goals of this study are to assess differences between treatment groups for the following:

1. Time to death from any cause
2. Time to first non-elective respiratory hospitalization
3. Time to first non-elective all-cause hospitalization
4. Total number of non-elective respiratory hospitalizations
5. Total number of non-elective all-cause hospitalizations
6. Change in FVC from randomization to 12 months
7. Change in DLCO from randomization to 12 months
8. Total number of respiratory infections
9. Change in UCSD-Shortness of Breath Questionnaire from randomization to 12 months
10. Change in Fatigue Severity Scale score from randomization to 12 months
11. Change in Leicester Cough Questionnaire score from randomization to 12 months
12. Change in EQ-5D score and SF-12 score from randomization to 12 months
13. Change in ICEpop CAPability measure for Older people (ICECAP-O) score from randomization to 12 months

## VII. Endpoint Descriptions

---

### **Primary Endpoint**

Endpoint Description: Time to first non-elective, respiratory hospitalization or all-cause mortality.

Response Variable Definition: Time to first respiratory hospitalization or all-cause mortality (primary endpoint) will be defined as the time to first observed event respiratory hospitalization or all-cause mortality. All patients will have some information regarding mortality and last visit of follow-up. Patients without any observed respiratory hospitalization or death event at the time of analysis will be censored at their last visit or lung transplantation. The respiratory hospitalizations will be reviewed and adjudicated by a clinical events committee (CEC).

Additional Covariates: Age, sex, baseline DLCO, baseline FVC, use of NAC at enrollment, use of standard of care medications at enrollment, and choice of antimicrobial agent prior to randomization. Note that the baseline DLCO and baseline FVC will be added to regression models using the % predicted versions for all endpoints.

Handling of Dropouts and Missing Data:

The censoring mechanism is assumed to be non-informative. Supportive analyses will be performed to assess the impact of a potential informative censoring.

Diagnostic tests: The additional continuous covariates to be used in the primary analysis model will be assessed for major departures from linearity by inspection of restricted cubic spline plots. If a departure is observed then a suitable transformation

will be explored. In addition the proportional hazard assumptions will be explored by inspection of Martingale residuals plots for all model covariates. If a major departure is observed then the variable will added to the model as a stratification variable.

Statistical Tests: The Cox proportional hazards regression model will be used to estimate outcome differences between the two treatment arms: “Standard care + oral antimicrobial therapy” and “Standard care”. The outcome is the time to first non-elective, respiratory hospitalization or all-cause mortality with model terms for treatment arm, baseline measurement, and covariates. Hazard ratios and 95% confidence intervals will summarize the differences between treatment arms.

Interpretation of Results: For Cox regression models a hazard ratio below 1.00 will indicate a reduction in events for “Standard care + oral antimicrobial therapy” arm. A hazard ratio above 1.00 will indicate increase in events for “Standard care + oral antimicrobial therapy” arm.

Alternative Analysis: To explore therapy crossovers an alternative analysis scenario will be constructed. Therapy crossover will be defined as patients assigned “Standard care” and receiving after randomization “oral antimicrobial therapy”. The previous presented primary analysis model will be used and modified. Specifically the response variable definition for the “Standard care” assigned patients (with crossover) will be changed such that the time to event and event indicator variables will be censored at the time of therapy crossover. The same statistical model and interpretation will be used as the primary analysis.

## VIII. Secondary Endpoint Descriptions

---

### **Secondary Endpoint #1**

Endpoint Description: Time to death from any cause.

Response Variable Definition: Time to death will be defined as the time to all-cause mortality. All patients will have some information regarding mortality and last visit of follow-up. Patients without any observed death at the time of analysis will be censored at their last visit or lung transplantation.

Additional Covariates: Age, sex, baseline DLCO, baseline FVC, use of NAC at enrollment, use of standard of care medications at enrollment, and choice of antimicrobial agent prior to randomization.

Handling of Dropouts and Missing Data: The censoring mechanism is assumed to be non-informative. Supportive analyses will be performed to assess the impact of a potential informative censoring.

Diagnostic tests: The additional continuous covariates to be used in the primary analysis model will be assessed for major departures from linearity by inspection of restricted cubic spline plots. If a departure is observed then a suitable transformation will be explored. In addition the proportional hazard assumptions will be explored by

inspection of Martingale residuals plots. If a major departure is observed then the variable will be added to the model as a stratification variable.

Statistical Tests: The Cox proportional hazards regression model will be used to estimate outcome differences between the two treatment arms: “Standard care + oral antimicrobial therapy” and “Standard care”. The outcome is the time to death from any cause with model terms for treatment arm, baseline measurement, and covariates. Hazard ratios and 95% confidence intervals will summarize the differences between treatment arms.

Interpretation of Results: For Cox regression models a hazard ratio below 1 will indicate a reduction in events for “Standard care + oral antimicrobial therapy” arm. A hazard ratio above 1.00 will indicate increase in events for “Standard care + oral antimicrobial therapy” arm.

## **Secondary Endpoint #2**

Endpoint Description: Time to first non-elective respiratory hospitalization

Response Variable Definition: Time to first non-elective respiratory hospitalization will be defined as the time to first non-elective respiratory hospitalization. The hospitalizations will be reviewed and adjudicated by a CEC as non-elective respiratory hospitalizations. All patients will have some information regarding mortality and last visit of follow-up. Patients without any observed event at the time of analysis will be censored at their last visit, death, or lung transplantation.

Additional Covariates: Age, sex, baseline DLCO, baseline FVC, use of NAC at enrollment, use of standard of care medications at enrollment, and choice of antimicrobial agent prior to randomization.

Handling of Dropouts and Missing Data: The censoring mechanism is assumed to be non-informative. Supportive analyses will be performed to assess the impact of a potential informative censoring.

Diagnostic tests: The additional continuous covariates to be used in the primary analysis model will be assessed for major departures from linearity by inspection of restricted cubic spline plots. If a departure is observed then a suitable transformation will be explored. In addition the proportional hazard assumptions will be explored by inspection of Martingale residuals plots. If a major departure is observed then the variable will be added to the model as a stratification variable.

Statistical Tests: The Cox proportional hazards regression model will be used to estimate outcome differences between the two treatment arms: “Standard care + oral antimicrobial therapy” and “Standard care”. The outcome is the time to first non-elective respiratory hospitalization with model terms for treatment arm, baseline measurement, and covariates. Hazard ratios and 95% confidence intervals will summarize the differences between treatment arms.

Interpretation of Results: For Cox regression models a hazard ratio below 1.00 will indicate a reduction in events for “Standard care + oral antimicrobial therapy” arm. A

hazard ratio above 1.00 will indicate increase in events for “Standard care + oral antimicrobial therapy” arm.

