11.3 Sample Size Justification

Based on prior work from the study team using IPFnet data, it is anticipated that the event rate in the placebo arm will be highly dependent on the proportion of patients enrolled at the different GAP scores. Given the availability of two FDA-approved drugs for IPF, it is our belief that the study population will be heavily weighted toward GAP scores of 3. In **Table 1**, the statistical power is determined for designs enrolling 500 patients with placebo group events rates varying from 24% to 36% and (12-month) treatment effects varying from 30% to 35%. In

general, the proposed design provides adequate power expect when the 12-month standard-of-care group event rate is 24% and the reduction in events is less than 30%.

Table 1. Statistical Power Assuming a Sample Size of 500 Randomized Patients

Standard-of-care event rate*	Antimicrobial therapy strategy event rate*	One-year Event Rate Reduction	Power
24%	16.8%	30%	78%
30%	21.0%	30%	87%
36%	25.2%	30%	93%
24%	16.0%	33.3%	86%
30%	20.0%	33.3%	93%
36%	24.0%	33.3%	97%
24%	15.6%	35%	89%
30%	19.5%	35%	95%
36%	23.4%	35%	98%

*12-month event rates. Calculations assume a 2-sided Type-I error rate of 0.05. The minimum follow-up is planned to be 12 months and the maximum follow-up is 42 months. Drop-out rates are assumed to be approximately 2% per year. Power calculations were based on a log-rank test with assumed event rates were exponentially distributed. Calculations were computing using nQuery 7.0 software.

We plan to enroll 500 patients over a 30 month window with a minimum of 12 months of follow-up on all patients. **Table 2** shows the required number of endpoint events to have 80% to 90% power with hazard ratios varying from 0.50 to 0.75.

Table 2. Required number of events

	HR=0.50	HR=0.55	HR=0.60	HR=0.65	HR=0.70	HR=0.75
80% power	65	88	120	169	247	379
85% power	75	100	138	194	282	434
90% power	87	118	161	226	330	508

Calculations performed using nQuery 7.0 and assume a 0.05 type I error rate (two-sided) with 1:1 randomization.

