Kaplan-Meier Event Rate (95% CI) At 24 Months	xx.x (xx.x, xx.x)	xx.x (xx.x, xx.x)	xx.x (xx.x, xx.x)	x.xxx
# of events/# of Patients	N/N	N/N	N/N	
Kaplan-Meier Event Rate (95% CI)	xx.x (xx.x, xx.x)	xx.x (xx.x, xx.x)	xx.x (xx.x, xx.x)	
Non-elective hospitalization				
Patients with one of more Number per patient	N (xx.x%)	N (xx.x%)	N (xx.x%)	
0	N (xx.x%)	N (xx.x%)	N (xx.x%)	
1	N (xx.x%)	N (xx.x%)	N (xx.x%)	
2	N (xx.x%)	N (xx.x%)	N (xx.x%)	
3	N (xx.x%)	N (xx.x%)	N (xx.x%)	
At 6 Months				x.xxx
# of events/# of Patients	N/N	N/N	N/N	
Kaplan-Meier Event Rate (95% CI)	xx.x (xx.x, xx.x)	xx.x (xx.x, xx.x)	xx.x (xx.x, xx.x)	
At 12 Monthss				x.xxx
# of events/# of Patients	N/N	N/N	N/N	
Kaplan-Meier Event Rate (95% CI)	xx.x (xx.x, xx.x)	xx.x (xx.x, xx.x)	xx.x (xx.x, xx.x)	
At 18 Months				x.xxx
# of events/# of Patients	N/N	N/N	N/N	
Kaplan-Meier Event Rate (95% CI)	xx.x (xx.x, xx.x)	xx.x (xx.x, xx.x)	xx.x (xx.x, xx.x)	
At 24 Months				x.xxx
# of events/# of Patients	N/N	N/N	N/N	
Kaplan-Meier Event Rate (95% CI)	xx.x (xx.x, xx.x)	xx.x (xx.x, xx.x)	xx.x (xx.x, xx.x)	
Respiratory hospitalization				
Patients with one of more Number per patient	N (xx.x%)	N (xx.x%)	N (xx.x%)	
0	N (xx.x%)	N (xx.x%)	N (xx.x%)	
1	N (xx.x%)	N (xx.x%)	N (xx.x%)	
2	N (xx.x%)	N (xx.x%)	N (xx.x%)	
3	N (xx.x%)	N (xx.x%)	N (xx.x%)	

**CLEANUP-IPF Study  
Final Analysis Table 3.1  
Primary Efficacy  
Summary of Events**

Event	Oral antimicrobial therapy N= N NEVAL	Standard Care N= N NEVAL	All Patients N= N NEVAL	P-Value
At 6 Months				x.xxx
# of events/# of Patients	N/N	N/N	N/N	
Kaplan-Meier Event Rate (95% CI)	xx.x (xx.x, xx.x)	xx.x (xx.x, xx.x)	xx.x (xx.x, xx.x)	
At 12 Monthss				x.xxx
# of events/# of Patients	N/N	N/N	N/N	
Kaplan-Meier Event Rate (95% CI)	xx.x (xx.x, xx.x)	xx.x (xx.x, xx.x)	xx.x (xx.x, xx.x)	
At 18 Months				x.xxx
# of events/# of Patients	N/N	N/N	N/N	
Kaplan-Meier Event Rate (95% CI)	xx.x (xx.x, xx.x)	xx.x (xx.x, xx.x)	xx.x (xx.x, xx.x)	
At 24 Months				x.xxx
# of events/# of Patients	N/N	N/N	N/N	
Kaplan-Meier Event Rate (95% CI)	xx.x (xx.x, xx.x)	xx.x (xx.x, xx.x)	xx.x (xx.x, xx.x)	
Respiratory infections				
Patients with one of more	N (xx.x%)	N (xx.x%)	N (xx.x%)	
Number per patient				
0	N (xx.x%)	N (xx.x%)	N (xx.x%)	
1	N (xx.x%)	N (xx.x%)	N (xx.x%)	
2	N (xx.x%)	N (xx.x%)	N (xx.x%)	
3	N (xx.x%)	N (xx.x%)	N (xx.x%)	

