**Final Analysis Table 3.1.3**  
**Primary Efficacy**  
**Time to first 1st Respiratory hospitalization**  
**Kaplan-Meier Plot**

**CLEANUP-IPF Study**  
**Final Analysis Table 3.1.4**  
**Primary Efficacy**  
**Time to first 1st Non-elective hospitalization**  
**Kaplan-Meier Plot**

**CLEANUP-IPF Study  
Final Analysis Table 3.2  
Primary Efficacy  
Model Analysis**

Comparison	Estimate with 95% Confidence Interval	Test Statistic	Nominal P-Value
Time to 1st Respiratory hospitalization or Death			
Hazard ratio of Oral antimicrobial therapy vs. Standard Care	xx.xx (xx.xx, xx.xx)	xx.xx	x.xxx
Time to first 1st Respiratory hospitalization			
Hazard ratio of Oral antimicrobial therapy vs. Standard Care	xx.xx (xx.xx, xx.xx)	xx.xx	x.xxx
Time to first 1st Non-elective hospitalization			
Hazard ratio of Oral antimicrobial therapy vs. Standard Care	xx.xx (xx.xx, xx.xx)	xx.xx	x.xxx
Total Respiratory hospitalizations			
Rate of Oral antimicrobial therapy	xx.xx (xx.xx, xx.xx)	xxx.xx	
Rate of Standard Care	xx.xx (xx.xx, xx.xx)	xxx.xx	
Ratio of Oral antimicrobial therapy vs. Standard Care	xx.xx (xx.xx, xx.xx)	xx.xx	x.xxx
Total Non-elective hospitalizations			
Rate of Oral antimicrobial therapy	xx.xx (xx.xx, xx.xx)	xxx.xx	x.xxx
Rate of Standard Care	xx.xx (xx.xx, xx.xx)	xxx.xx	x.xxx
Ratio of Oral antimicrobial therapy vs. Standard Care	xx.xx (xx.xx, xx.xx)	xx.xx	x.xxx
Total Respiratory infections			
Rate of Oral antimicrobial therapy	xx.xx (xx.xx, xx.xx)	xxx.xx	x.xxx
Rate of Standard Care	xx.xx (xx.xx, xx.xx)	xxx.xx	x.xxx
Ratio of Oral antimicrobial therapy vs. Standard Care	xx.xx (xx.xx, xx.xx)	xx.xx	x.xxx

**CLEANUP-IPF Study  
Final Analysis Table 4.1.1  
Secondary Efficacy  
FVC and DLCO  
Descriptive Summary**

Parameter Visit Statistic	Oral antimicrobial therapy N= NEVAL	Standard Care N= NEVAL	All Patients N=NEVAL	P-Value
FVC (liters)				
Baseline				
N	xx	xx	xx	x.xxx
Mean (SD)	x.xx (xx.x)	x.xx (xx.x)	x.xx (xx.x)	
Median (Q1, Q3)	x.xx (x.xx, x.xx)	x.xx (x.xx, x.xx)	x.xx (x.xx, x.xx)	
Week 12				
N	xx	xx	xx	x.xxx
Mean (SD)	x.xx (xx.x)	x.xx (xx.x)	x.xx (xx.x)	
Median (Q1, Q3)	x.xx (x.xx, x.xx)	x.xx (x.xx, x.xx)	x.xx (x.xx, x.xx)	
Week 24				
N	xx	xx	xx	x.xxx
Mean (SD)	x.xx (xx.x)	x.xx (xx.x)	x.xx (xx.x)	
Median (Q1, Q3)	x.xx (x.xx, x.xx)	x.xx (x.xx, x.xx)	x.xx (x.xx, x.xx)	
FVC % Predicted				
Baseline				
N	xx	xx	xx	x.xxx
Mean (SD)	x.xx (xx.x)	x.xx (xx.x)	x.xx (xx.x)	

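### The Kaplan-Meier rates and plots for first hospitalization (SAP Table 3.1, plots 3.1.3 and 3.1.4) censor deaths and so overstate the proportion of patients hospitalized

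*SAP*

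**What the plan says.** SAP section VIII, Secondary Endpoints #2 and #3, states that patients without the event "will be censored at their last visit, death, or lung transplantation". Both sections add "The censoring mechanism is assumed to be non-informative", and both promise supportive analyses of possible informative censoring without saying what these are. The only analysis the two sections specify is a Cox model summarized by a hazard ratio.

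The absolute rates appear only in SAP section XV. Mock-up Table 3.1 has a block for non-elective hospitalization and one for respiratory hospitalization. At 6, 12, 18 and 24 months each block has a row labelled "Kaplan-Meier Event Rate (95% CI". Mock-ups 3.1.3 ("Time to first 1st Respiratory hospitalization") and 3.1.4 ("Time to first 1st Non-elective hospitalization") are Kaplan-Meier plots of the same two endpoints. Section XV says of its tables and figures that they "are the template versions and may be modified as needed".

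Neither document mentions competing risks or cumulative incidence. The addendum of 29 May 2020 changes the adjudication and coding rules and adds data cut-offs for sensitivity analyses. It does not touch these displays.

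**The concern.** A patient who dies without a prior hospitalization can no longer have one. Kaplan-Meier treats that patient as if still able to be hospitalized later, at the same rate as those who remain at risk. One minus Kaplan-Meier then describes hospitalization in a setting where nobody dies, whereas a reader of an event rate with a confidence interval, tabulated by arm, will take it as the percentage of trial patients hospitalized by that month.

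Death is not a rare competing event here. Protocol section 3 gives a median survival of 3-5 years after diagnosis, and death is a component of the primary endpoint. Two things are at stake: the absolute hospitalization percentages would be too high, and if mortality differs between arms the error would differ too, which would distort the comparison of the absolute rates.

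**Working it through.** **Inputs from the documents.** Protocol section 11.3, Table 1: 500 patients, 12-month composite rates of 24%, 30% and 36% under standard of care, exponential event times. Minimum follow-up is 12 months, accrual 30 months, dropout about 2% per year.

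**Input that is assumed.** The share *s* of composite first events that are deaths without a prior respiratory hospitalization. The documents do not split the composite. I use 15%, 25% and 35%.

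**Step 1: reproduce a stated figure.** For 30% versus 21.0%, the annual hazards are −ln(0.70) = 0.3567 and −ln(0.79) = 0.2357, so HR = 0.661. With follow-up uniform from 1 to 3.5 years and dropout hazard −ln(0.98) = 0.0202, 250 patients per arm give about 230 expected events. Power = Φ(|ln 0.661| × √230 / 2 − 1.96) = Φ(1.18) = 88%, against 87% in Table 1. Reading Table 1 as 12-month rates with constant hazards is therefore sound.

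**Step 2: the two estimands for endpoint #2.** With L = −ln(1 − 12-month composite rate) and *t* in years:

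- One minus Kaplan-Meier, deaths censored: 1 − exp(−L(1−s)t)
- Cumulative incidence (true proportion hospitalized): (1−s)(1 − exp(−Lt))

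Example with 30% and s = 25% at 24 months: 1 − exp(−0.3567 × 0.75 × 2) = 41.43%, against 0.75 × (1 − 0.70²) = 38.25%. The gap is 3.2 points.

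Overstatement in percentage points:

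| Composite 12-month rate | s | at 12 months | at 24 months |
|---|---|---|---|
| 24% | 15% | 0.4 | 1.4 |
| 24% | 25% | 0.6 | 2.1 |
| 24% | 35% | 0.7 | 2.5 |
| 30% | 15% | 0.7 | 2.1 |
| 30% | 25% | 1.0 | 3.2 |
| 30% | 35% | 1.2 | 4.0 |
| 36% | 15% | 1.0 | 3.0 |
| 36% | 25% | 1.4 | 4.5 |
| 36% | 35% | 1.8 | 5.6 |

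Widening *s* to 10-50% gives 0.3-2.0 points at 12 months and 1.0-6.5 at 24 months. A simulation of 400,000 patients at 30% and s = 30% agrees with the formulas: 39.4% by Kaplan-Meier against 35.7% truly hospitalized at 24 months.

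**Step 3: do the components add up?** At 30% and s = 30%, the 24-month composite is 1 − 0.70² = 51.0%. Cumulative incidence splits it exactly: 0.7 × 51.0 = 35.7% hospitalized first and 0.3 × 51.0 = 15.3% dying first. The Kaplan-Meier figure of 39.3% does not fit that split (39.3 + 15.3 = 54.6).

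**Step 4: unequal mortality, as an illustration.** Give both arms the same hospitalization hazard, 0.7 × 0.3567 = 0.2497, and death hazards of 0.1070 and twice that, 0.2140. Kaplan-Meier reads 1 − exp(−0.4993) = 39.3% at 24 months in both arms. The true proportions are 35.7% and (0.2497/0.4637) × (1 − exp(−0.9274)) = 32.5%. The doubling is hypothetical.

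**Endpoint #3.** Table 1 concerns respiratory hospitalization or death. It says nothing about all-cause hospitalization, so no size is calculated.

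**The case against.** *The censoring rule is right for what sections #2 and #3 analyse.* This stands. A Cox model that censors deaths estimates the cause-specific hazard ratio, a valid quantity. A reader might infer that the rule itself, the hazard ratios or the primary result is biased. The documents do not support that: the composite counts death as an event, and so does the mortality endpoint. Only the displayed hospitalization rates and curves are at fault.

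*The mock-ups are templates.* True, and section VIII does not itself commit to Kaplan-Meier displays. But the mock-ups are the only specification of these displays, and nothing in the text points elsewhere.

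*Supportive analyses are promised.* They are unspecified and aimed at informative censoring. The gap exists even when death is unrelated to hospitalization risk, as in the independent constant hazards above.

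*Table 3.1 also shows crude counts and mortality.* It does, so the rates are not shown alone. The crude counts ignore unequal follow-up and do not replace a time-specific rate.

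*The effect is small.* Largely fair. With 250 patients per arm, the 95% half-width is about 1.96 × √(0.22 × 0.78/250) = 5.1 points at a rate of 22%, and 1.96 × √(0.40 × 0.60/250) = 6.1 points at 40%, before allowing for censoring. The overstatement stays within that. Table 1's antimicrobial-arm rates, at most 25.2%, give smaller gaps: with s = 35% that rate gives 0.8 points at 12 months and 2.8 at 24. The error is nevertheless systematic and always upward.

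*The termination letter.* It mentions a trend toward higher mortality in the intervention arm, and a reader might infer that the arm comparison of hospitalization rates is in fact distorted. The letter gives no figures and reports no clear harm signal. It makes a differential error possible, no more.

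**Conclusion.** The concern holds for the displays. If the mock-ups are produced as written, the Kaplan-Meier rates and curves for endpoints #2 and #3 overstate the proportion of patients hospitalized. The direction needs no assumption beyond at least one at-risk patient dying before a hospitalization.

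The size is illustrative. For #2 it is about 0.4-1.8 points at 12 months and 1.4-5.6 at 24 months, resting on constant hazards, Table 1's control-arm composite rates and the assumed 15-35% death share. The median survival in Protocol section 3 cannot supply that share, because it also counts deaths after a hospitalization. It would be tempting to apply the same range to #3, but no figure in the documents supports that.

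The overstatement can differ by arm if mortality differs. This is a reporting error worth correcting and leaves the trial's main conclusion untouched.

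**What to change.** - In the two hospitalization blocks of Table 3.1 and in plots 3.1.3 and 3.1.4, replace Kaplan-Meier with Aalen-Johansen cumulative incidence and 95% confidence intervals, with death as a competing event.
- State that lung transplantation remains a censoring event for these displays, so that readers know what the proportion refers to.
- Keep the Cox models for #2 and #3 with their present censoring rule, and label the hazard ratios cause-specific.
- Keep Kaplan-Meier for the composite endpoint and for death.
- A Fine-Gray model or Gray test is optional. The problem lies in the absolute rates and needs no further test.

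The cost is a few sentences in the SAP and minor programming. No new data are needed, and the reported hospitalization percentages become somewhat lower.
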